3.6.2. Outliers

Outliers will be identified during the data management and data analysis process. All data, including outliers, will be included in analyses.

3.7. Data Handling Conventions and Transformations

In general, age (in years) on the date of the first dose of study drug will be used for analyses and presentation in listings. If an enrolled subject was not dosed with any study drug, the randomization date will be used instead of the first dosing date of study drug. For screen failures, the date the informed consent was signed will be used for age calculation. If only birth year is collected on the eCRF, “01 July” will be used for the unknown birth day and month for the purpose of age calculation. If only birth year and month are collected, “01” will be used for the unknown birth day.

Non-PK data that are continuous in nature but are less than the lower limit of quantitation (LOQ) or above the upper LOQ will be imputed as follows:

- A value that is 1 unit less than the LOQ will be used for calculation of descriptive statistics if the datum is reported in the form of “< x” (where x is considered the LOQ). For example, if the values are reported as < 50 and < 5.0, values of 49 and 4.9, respectively, will be used for calculation of summary statistics. An exception to this rule is any value reported as < 1 or < 0.1, etc. For values reported as < 1 or < 0.1, a value of 0.9 or 0.09, respectively, will be used for calculation of summary statistics.
- A value that is 1 unit above the LOQ will be used for calculation of descriptive statistics if the datum is reported in the form of “> x” (where x is considered the LOQ). Values with decimal points will follow the same logic as above.
- The LOQ will be used for calculation of descriptive statistics if the datum is reported in the form of “≤ x” or “≥ x” (where x is considered the LOQ).

When any ELF component (hyaluronic acid, procollagen III N-terminal propeptide [PIIINP] and tissue inhibitor of metalloproteinase 1 [TIMP1]) is less than the lower LOQ or above the upper LOQ, the ELF component will be imputed based on the rules described above, and the ELF test score will be calculated based on the imputed value of the component(s) as defined in [Appendix 7](#).

Natural logarithm transformation will be used for plasma concentrations and analysis of PK parameters. Plasma concentration values that are below the limit of quantitation (BLQ) will be presented as “BLQ” in the concentration data listing. Values that are BLQ will be treated as 0 at predose time points and one-half the value of the LOQ at postbaseline time points.

The following conventions will be used for the presentation of summary and order statistics:

- If at least 1 subject has a concentration value of BLQ for the time point, the minimum value will be displayed as “BLQ.”
- If more than 25% of the subjects have a concentration data value of BLQ for a given time point, the minimum and Q1 values will be displayed as “BLQ.”
- If more than 50% of the subjects have a concentration data value of BLQ for a given time point, the minimum, Q1, and median values will be displayed as “BLQ.”
- If more than 75% of the subjects have a concentration data value of BLQ for a given time point, the minimum, Q1, median, and Q3 values will be displayed as “BLQ.”
- If all subjects have concentration data values of BLQ for a given time point, all order statistics (minimum, Q1, median, Q3, and maximum) will be displayed as “BLQ.”

3.8. Analysis Visit Windows

3.8.1. Definition of Study Day

Study day/OL study day will be calculated from the first dosing date of study drug in the corresponding phase (Randomized or OL) and derived as follows:

- For postdose study days: Assessment Date – First Dosing Date + 1
- For days prior to the first dose: Assessment Date – First Dosing Date

Study Day 1/OL Study Day 1 is the day of first dose of study drug administration in the corresponding phase.

3.8.2. Analysis Visit Windows

Subject visits might not occur on protocol-specified days. Therefore, for the purpose of analysis, observations will be assigned to analysis windows.

On-treatment visit windows will be calculated from Study Day 1/OL Study Day 1 for selected efficacy measures, vital signs, elastography, and safety laboratory data.

Selected safety and efficacy data, unless otherwise specified, collected up to and including the last dosing date in the Randomized Phase + 30 days and before OL Study Day 1 for the Randomized Phase, whichever is earlier, or OL last dosing date + 30 days for the OL Phase, will be mapped according to the following analysis windows unless the nominal visit name is Follow-Up or OL Follow-Up.

All biopsy data and elastography data collected will be mapped to Randomized Phase visit windows unless on or after OL Study Day 1. HRQoL questionnaires and HRUQ will not be windowed, and will be summarized by nominal visit. For those endpoints, missing (OL) Baseline/Day 1 values will not be imputed.

The analysis windows for select measures are provided in [Table 3-1](#) to [Table 3-6](#).

Table 3-1. Analysis Visit Windows for Chemistry, Hematology, Coagulation, CP/MELD scores, Vital Signs, Body Weight, and Stool Frequency

Analysis Visit	Nominal Day	Lower Limit	Upper Limit
Baseline/OL-Baseline	1	(none)	1
Week 1/OL-Week 1	8	2	18
Week 4/OL-Week 4	29	19	42
Week 8/OL-Week 8	57	43	70
Week 12/OL-Week 12	85	71	98
Week 16/OL-Week 16	113	99	126
Week 20/OL-Week 20	141	127	154
Week 24/OL-Week 24	169	155	182
Week 28/OL-Week 28	197	183	210
Week 32/OL-Week 32	225	211	238
Week 36/OL-Week 36	253	239	266
Week 40/OL-Week 40	281	267	294
Week 44/OL-Week 44	309	295	322
Week 48/OL-Week 48	337	323	378
Week 60/OL-Week 60	421	379	462
Week 72/OL-Week 72	505	463	546
Week 84/OL-Week 84	589	547	630
Week 96/OL-Week 96	673	631	714
Week 108/OL-Week 108	757	715	798
Week 120/OL-Week 120	841	799	882
Week 132/OL-Week 132	925	883	966
Week 144/OL-Week 144	1009	967	1050
Week 156/OL-Week 156	1093	1051	1134
Week 168/OL-Week 168	1177	1135	1218
Week 180/OL-Week 180	1261	1219	1302
Week 192/OL-Week 192	1345	1303	1386
Week 204/OL-Week 204	1429	1387	1470
Week 216/OL-Week 216	1513	1471	1554
Week 228/OL-Week 228	1597	1555	1638
Week 240/OL-Week 240	1681	1639	≥1681

Table 3-2. Analysis Visit Windows for Waist Circumference, Insulin, Homeostasis Model Assessment of Insulin Resistance (HOMA-IR), Lipids and Hemoglobin A1c

Analysis Visit	Nominal Day	Lower Limit	Upper Limit
Baseline/OL-Baseline	1	(none)	1
Week 4/OL-Week 4	29	2	56
Week 12/OL-Week 12	85	57	126
Week 24/OL-Week 24	169	127	252
Week 48/OL-Week 48	337	253	420
Week 72/OL-Week 72	505	421	588
Week 96/OL-Week 96	673	589	756
Week 120/OL-Week 120	841	757	924
Week 144/OL-Week 144	1009	925	1092
Week 168/OL-Week 168	1177	1093	1260
Week 192/OL-Week 192	1345	1261	1428
Week 216/OL-Week 216	1513	1429	1596
Week 240/OL-Week 240	1681	1597	≥1681

Table 3-3. Analysis Visit Windows for ELF test score and components, FibroSure/FibroTest, α -Macroglobin, Haptoglobin, Apolipoprotein A1, C-Reactive Protein (CRP) and Total Bile Acids

Analysis Visit	Nominal Day	Lower Limit	Upper Limit
Baseline/OL-Baseline	1	(none)	1
Week 12/OL-Week 12	85	2	126
Week 24/OL-Week 24	169	127	252
Week 48/OL-Week 48	337	253	420
Week 72/OL-Week 72	505	421	588
Week 96/OL-Week 96	673	589	756
Week 120/OL-Week 120	841	757	924
Week 144/OL-Week 144	1009	925	1092
Week 168/OL-Week 168	1177	1093	1260
Week 192/OL-Week 192	1345	1261	1428
Week 216/OL-Week 216	1513	1429	1596
Week 240/OL-Week 240	1681	1597	≥1681

Table 3-4. Analysis Visit Windows for Elastography and Pooled Cohort Risk and Score

Analysis Visit	Nominal Day	Lower Limit	Upper Limit
Baseline	1	(none)	1 (28*)
Week 24	169	2(29*)	252
Week 48	337	253	420
Week 72	505	421	588
Week 96	673	589	840
Week 144	1009	841	1176
Week 192	1345	1177	1512
Week 240	1681	1513	≥1681

* for Elastography.

Table 3-5. Analysis Visit Windows for Cytokeratin-18 (CK-18) M30 and CK-18 M65

Analysis Visit	Nominal Day	Lower Limit	Upper Limit
Baseline	1	(none)	1
Week 24	169	2	252
Week 48	337	253	504
Week 96	673	505	840
Week 144	1009	841	1176
Week 192	1345	1177	1512
Week 240	1681	1513	≥1681

Table 3-6. Analysis Visit Windows for Biopsy Data

Analysis Visit	Nominal Day	Lower Limit	Upper Limit
Baseline	1	(none)	1
Week 48	337	169	504
Week 240	1681	505	≥1681

Data relating to unscheduled visits and early termination visits may be assigned to a particular visit or time point based on the visit windows. The following conventions will be followed:

- An unscheduled visit prior to the first dosing of study drug may be included in the calculation of the baseline value, if applicable.
- Unscheduled visits after the first dose of study drug will be included in determining the maximum postbaseline toxicity grade.
- Data collected on a follow-up visit will be summarized as a separate visit, and labeled “Follow-up Visit” for each phase.

3.8.3. Selection of Data in the Event of Multiple Records in an Analysis Visit Window

Depending on the statistical analysis method, single values may be required for each analysis window. For example, change from baseline by visit usually requires a single value, whereas a time-to-event analysis would not require 1 value per analysis window.

If multiple, valid, nonmissing, continuous measurements exist in an analysis window, records will be chosen based on the following rules if a single value is needed:

- In general, the baseline value will be the last nonmissing value on or prior to the first dosing date of study drug in the corresponding phase. If multiple measurements occur on the same day, the last nonmissing value prior to the time of first dosing of study drug will be considered as the baseline value. If these multiple measurements occur at the same time or the time is not available, the average of these measurements (for continuous data) will be considered as the baseline value. Baseline values for liver tests (ALT, AST, total bilirubin and direct bilirubin) in the Randomized Phase will be determined by averaging the values obtained between and including Screening and Day 1; baseline values for liver tests (ALT, AST, total bilirubin, and direct bilirubin) in the OL Phase will be determined by averaging the values obtained between OL Study Day - 55 and OL Study Day 1 (inclusive); baseline values for elastography will be determined as the last nonmissing values on or prior to (OL) Day 28. Missing (OL) Baseline/Day 1 values of HRQoL questionnaires and HRUQ will not be imputed.
- For postbaseline visits:
 - 1) The record closest to the nominal day for that visit will be selected.
 - 2) If there are 2 records that are equidistant from the nominal day, the later record will be selected.
 - 3) In general, if there is more than 1 record on the selected day, the average will be taken. For serum creatinine, if both enzymatic and regular creatinine are collected from the same blood sample and are analyzable, regular creatinine will be selected for analysis.

If multiple, valid, nonmissing, categorical measurements exist in an analysis window, records will be chosen based on the following rules if a single value is needed:

- For baseline, the last available record on or prior to the date of the first dose of study drug will be selected in the corresponding phase. If there are multiple records on the same day, the value with the lowest severity will be selected (eg, normal will be selected over abnormal for safety electrocardiogram [ECG] findings).
- For postbaseline visits, if there are multiple records on the same day, the value with the worst severity within the window will be selected (eg, abnormal will be selected over normal for safety ECG findings).

Postbaseline parameters used to define histology endpoints will be selected in each visit window according to the following rules:

- Histology endpoints including a ≥ 1 -stage improvement in fibrosis without worsening of NASH, progression to cirrhosis, ≥ 1 -stage improvement in fibrosis, NASH resolution without worsening of fibrosis, NAS and elements, SAF and elements will be derived based on parameters collected from 1 biopsy sampling date if the following 4 parameters are available: NASH CRN fibrosis stage, lobular inflammation, hepatocellular ballooning, and steatosis grades.
- When the set of the 4 parameters (NASH CRN fibrosis stage, lobular inflammation, hepatocellular ballooning, and steatosis grades) is available for multiple biopsy samples obtained on different dates in 1 visit window, the set with the biopsy sample collection date closest to the nominal day will be chosen for analysis.. When 2 samples are equidistant from the nominal day, the later set will be selected.
- When the set of the 4 parameters is not complete for any biopsy sample from a single day, the histology endpoints will be derived based on the nonmissing value of each individual parameter closest to the nominal day for that visit window. When 2 records are equidistant from the nominal day, the later record will be selected.
- For Ishak fibrosis stage, the nonmissing value from the biopsy sample collection date closest to the nominal day for the visit window will be selected regardless of the missing status of other parameters. When 2 records are equidistant from the nominal day, the later record will be selected.
- When an endpoint cannot be derived based on all biopsy samples in a visit window, the histology endpoint will be considered missing, and imputation methods listed in Section 3.6.1 will apply.

Liver stiffness by transient elastography data in each analysis visit window will be chosen based on the following rules:

- For baseline, measurements by XL probe will be selected for analysis if available; otherwise measurements by M probe will be selected.
- For postbaseline visits, measurements by the same probe type (XL or M) selected for the subject at baseline will be selected in each analysis visit window. If no measurement by the same probe type as baseline is available, the analysis value for the corresponding postbaseline visit will be considered missing. If there are multiple postbaseline records by the same probe type as baseline, the rules to choose postbaseline continuous measurements as described above will apply.

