**Key Exclusion Criteria**

- 1) Prior history of decompensated liver disease including ascites, HE, or variceal bleeding
- 2) CP score  $> 6$ , as determined at Screening, unless due to therapeutic anti-coagulation
- 3) MELD score  $> 12$ , as determined at Screening, unless due to therapeutic anti-coagulation

- 4) Chronic hepatitis B virus (HBV) infection (hepatitis B surface antigen [HBsAg] positive)
- 5) Chronic hepatitis C virus (HCV) infection (HCV Ab and HCV ribonucleic acid [HCV RNA] positive). Subjects cured of HCV infection less than 5 years prior to the Screening visit are not eligible
- 6) Other causes of liver disease including, but not limited to, alcoholic liver disease, hepatitis B, hepatitis C, autoimmune disorders (e.g., primary biliary cholangitis, primary sclerosing cholangitis, and autoimmune hepatitis), drug-induced hepatotoxicity, Wilson disease, iron overload, and alpha-1-antitrypsin deficiency, based on medical history and/or centralized review of liver histology
- 7) History of liver transplantation
- 8) Current or history of HCC
- 9) Any weight reduction surgery in the 2 years prior to Screening or planned during study (weight reduction surgery is disallowed during the study), and malabsorptive weight loss surgery (e.g., Roux-en-Y or distal gastric bypass) at any time prior to Screening
- 10) Weight loss > 10% within 6 months of Screening
- 11) Human immunodeficiency virus (HIV) infection
- 12) Unstable cardiovascular disease

Study  
Procedures/  
Frequency:

Screening assessments will include complete medical history, physical exam (PE), vital signs, laboratory assessments, pregnancy tests (for females of child-bearing potential), liver biopsy (if required), standard 12-lead electrocardiogram (ECG), CCI [REDACTED] and review of adverse events (AEs) and concomitant medications.

Eligible subjects will be randomized to one of the three treatment groups: SEL 6 mg, SEL 18 mg or placebo to match (PTM). Prior to initial dosing, the following Day 1 assessments will be performed: symptom driven PE, vital signs, laboratory assessments, pregnancy tests (for females of child-bearing potential), liver stiffness measurement by elastography (if available), stool frequency assessment, Health Related Quality of Life (HRQoL) and Health Resource Utilization questionnaires, and review of AEs and concomitant medications.

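### The elastography baseline rule lets a scan from Days 2–28 replace a valid pre-dose scan, when it should be used only where no pre-dose scan exists (minor).

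*SAP*

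**What the plan says.** SAP Section 3.8.3 gives a general rule: "In general, the baseline value will be the last nonmissing value on or prior to the first dosing date of study drug" in the relevant phase. The same bullet then makes an exception: "baseline values for elastography will be determined as the last nonmissing values on or prior to (OL) Day 28". SAP Section 3.8.1 fixes the time origin: "Study Day 1/OL Study Day 1 is the day of first dose of study drug administration in the corresponding phase".

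Table 3-4 in SAP Section 3.8.2 carries the exception through. The baseline window ends on Day 1, or on Day 28 where the asterisk applies. The Week 24 window opens on Day 2, or on Day 29 with the asterisk. The asterisk is explained as "for Elastography".

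The protocol synopsis (Study Procedures/Frequency) introduces the Day 1 procedures with "Prior to initial dosing, the following Day 1 assessments will be performed", and the list includes "liver stiffness measurement by elastography (if available), stool frequency assessment". Protocol Section 6.4.2 places the next elastography at Week 24, and the table in Appendix 2 agrees. That table also shows elastography at Screening. The footnotes on the Screening and Day 1 cells are redacted.

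For transient elastography, the last part of SAP Section 3.8.3 selects the XL-probe reading at baseline if there is one and the M-probe reading otherwise. It then ties later visits to the probe chosen at baseline.

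**The concern.** A baseline value should come before treatment. The general rule ensures this, and the ELF and CK-18 windows (Tables 3-3 and 3-5) close on Day 1. So does the pooled cohort score, which shares Table 3-4 with elastography. The convention on unscheduled visits in SAP Section 3.8.2 also looks only backwards: "An unscheduled visit prior to the first dosing of study drug may be included in the calculation of the baseline value".

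Accepting a late first scan from a subject who has no earlier one is a reasonable rescue. The elastography rule goes further, because it asks for the latest value up to Day 28 whether or not a pre-dose value is on file. Two things follow for a subject who has both:

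- A post-randomisation reading is reported as a baseline characteristic. SAP Section 5.2 lists liver stiffness by transient elastography among these.
- Any drug effect already present at that reading is subtracted from later change, which pulls the SEL–placebo difference towards zero.

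The probe rule leaves a second gap. It states no preference for pre-dose records, so an XL reading from Days 2–28 could displace a Day 1 M-probe reading and then decide which probe counts at every later visit.

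**Working it through.** The documents give no sample size, power or significance level for elastography, so there is no plan figure to reproduce. The check compares the texts and then works out the effect for one affected subject.

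**1. Which value becomes baseline**

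| Scans on file | General rule | Elastography rule |
|---|---|---|
| Pre-dose only | Pre-dose | Pre-dose |
| Days 2–28 only | None | Latest of Days 2–28 |
| Pre-dose and Days 2–28 | Pre-dose | Latest of Days 2–28 |

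The second row is the rescue case. The third row is the defect: a valid pre-dose value exists and is not used. The window contains 28 − 1 = 27 days after the day of first dose.

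**2. What is absorbed for a subject in the third row**

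Let E(t) be the drug effect on stiffness at study day t, with E(1) = 0. Measured from a pre-dose baseline, the effect on change at day v is E(v). Measured from a scan on day d, it is E(v) − E(d). The share lost is E(d)/E(v). If onset is linear from Day 1 (an assumption; the documents give no time course), this is (d − 1)/(v − 1).

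Inputs: nominal days v = 169 (Week 24) and v = 337 (Week 48) from Table 3-4, and d within 2 to 28.

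| Baseline scan on day d | Week 24 | Week 48 |
|---|---|---|
| 2 | 1/168 = 0.6% | 1/336 = 0.3% |
| 14 | 13/168 = 7.7% | 13/336 = 3.9% |
| 28 | 27/168 = 16.1% | 27/336 = 8.0% |

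A faster onset would raise these shares and a delayed one would lower them.

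**3. From one subject to the trial**

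The trial-level loss avoided by the fix would be the per-subject share multiplied by the proportion of subjects who have both kinds of scan. The documents do not give that proportion. For subjects scanned on schedule, the loss is zero.

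**The case against.** The strongest reply is that the override needs an extra scan. The visible schedule goes from Day 1 to Week 24 with no elastography between. Because elastography is done only where available, the usual Day 2–28 record would be a late first scan with nothing earlier to displace. The paired Day 28 and Day 29 limits show that the allowance is deliberate, and the redacted footnotes may contain a timing rule that explains it. Elastography does not enter the primary histology endpoint, EFS or the listed secondary endpoints, and the error dilutes a difference rather than favouring SEL. The probe preference could also work the other way and keep a pre-dose XL reading over a later M-probe one.

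All of this stands as a limit on the importance of the point, and it rules out several stronger readings:

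- **That on-treatment baselines are the general result of the rule.** They arise only from late or unscheduled scans.
- **That a trial-wide percentage of dilution can be quoted.** One could multiply the per-subject share by an assumed proportion of subjects with a Day 2–28 baseline. The documents give no such proportion. It would also count rescue subjects, whose values the fix keeps in the main analysis.
- **That the SAP contradicts the protocol.** With the footnotes redacted, this cannot be settled.
- **That the noninvasive-marker analyses are contaminated.** SAP Section 6.5 moves them to a separate plan that is not among the documents, and the exploratory endpoints are redacted. The visible use is the baseline table.
- **That the open-label baseline needs the same repair.** SAP Section 6 excludes open-label data from efficacy analyses, Section 5.2 does not list stiffness among the open-label baseline characteristics, and Table 3-4 has no open-label windows.

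None of this supplies a reason to discard a pre-dose value that is already on file.

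**Conclusion.** The point holds as a minor defect of wording. As written, SAP Section 3.8.3 and Table 3-4 replace a valid pre-dose elastography value with an on-treatment one whenever a subject has both. For such a subject, the largest absorption under linear onset is about 16% of the Week 24 effect and 8% of the Week 48 effect. Both figures rest on the assumed onset and on a scan as late as Day 28. The number of subjects affected is unknown and the overall effect is probably small. No visible confirmatory conclusion depends on it.

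**What to change.** In SAP Section 3.8.3 and Table 3-4, define the Randomized Phase elastography baseline as the latest available value on or before first dose. Only if there is none, use the earliest value on Days 2–28. Flag these subjects, count them by arm, and repeat any analysis of change in elastography without them.

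In the probe rule of SAP Section 3.8.3, state that pre-dose records are selected first and the XL-over-M preference is applied among them.

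The cost is a few lines of SAP text and a small programming change. No new data are needed and no subject leaves the main analysis. Since the SAP is signed, its Section 1 provides the route: document the change in the clinical study report.
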